5.8 Data to be Collected

5.8.1 Patient Information to Be Collected Prior to Initiation of Treatment

The following data will be collected and recorded on the Case Report Forms for Screening.

- 1. Coded Patient I.D.
- 2. Inclusion/Exclusion Criteria
- 3. Signed Patient Informed Consent
- 4. Patient Demographics
 - a. Gender
 - b. Date of Birth
 - c. Hospital Admission Weight, Height, and Body Surface Area
 - d. Calculated Intravascular Blood Volume
- 5. Patient Medical Information
 - a. Cause of Acute Kidney Injury

- b. Diagnosis
- c. Vital Signs
- d. Medication History for the Last 7 Days
- e. Medical and Surgical History

5.8.2 Treatment Data to Be Collected

The following data will be collected and recorded on the eCRFs and/or data card for each patient treatment using the Gambro Prismaflex HF20 Set and Prismaflex System Software Version 7.10 and 7.20.

5.8.2.1 Treatment Information

- 1. Date of Treatment
- 2. Sequential Number of Gambro Prismaflex[®] HF20 Sets used
- 3. Date and Time of Treatment Initiation and Discontinuation
- 4. Blood access information
- 5. Treatment Modality
 - a. CVVHD (Hemodialysis)
 - b. CVVHDF (Hemofiltration)
 - c. CVVH (Hemofiltration)

5.8.2.2 Treatment Prescription

- 1. Patient Fluid Removal Flow Rate (ml/h)
- 2. Replacement Flow Rate (ml/h)
- 3. Blood Flow Rate (ml/min)
- 4. Dialysate Flow Rate (ml/h)
- 5. Pre-blood pump (PBP) Flow rate (ml/h)

5.8.2.3 Dialysate, Pre-blood Pump (PBP) and Replacement Solutions Used

- 1. Ionic Formulation
- 2. Brand Name
- 3. Volume used

5.8.2.4 Priming Solution(s) (volume and infusion rate)

- 1. Blood
- 2. Buffered Blood
- 3. Saline
- 4. Heparinized Saline
- 5. Albumin

5.8.2.5 Anticoagulation Information

- 1. Type of anticoagulant used
- 2. Administration method
- 3. Anticoagulant dose

5.8.2.6 Patient Clotting Parameters

1. ACT, PTT, APTT, or other according to Sampling Schedule in Section 5.9.

5.8.2.7 Treatment Blood & Dialysate Concentration Data

- Blood Urea Nitrogen (BUN) according to the Sampling Schedule in Section 5.9.
- Fluid Urea Nitrogen (FUN) according to the Sampling Schedule in Section 5.9.
- 3. Creatinine according to the Sampling Schedule in Section 5.9.
- 4. Bicarbonate according to the Sampling Schedule in Section 5.9.
- 5. Serum sodium, potassium, chloride, calcium, phosphorous, beta 2 microglobulin (B2M) & albumin according to the Sampling Schedule in Section 5.9.
- 6. Dialysate fluid urea nitrogen (FUN) according to the Sampling Schedule in Section 5.9

5.8.2.8 Information on Interruptions/Filter Changes and Blood Loss

- 1. Reason(s) for filter change
- 2. Start time and Stop time of interruption.
- 3. Filter duration within treatment before clotting

- 4. Reason for interruption/Filter change
- 5. Complications related to filter clotting and associated AE (if applicable)
 - a. Transfusion requirements
 - b. Estimated blood loss

5.8.2.9 Total Fluid Removal, Fluid Overload, Blood & Mean Arterial Pressures

- 1. Amount (cumulative total) of fluid removed
- 2. End of study weight
- 3. Fluid overload at CRRT initiation and at 12 hour intervals up to end of study or 72 hours of CRRT according to the schedule in Table 2
- 4. Blood pressure including mean arterial pressure at admission to the ICU, at CRRT initiation and at hourly intervals up to end of study or 72 hours of CRRT according to the schedule in Table 2
- 5. Periodic Patient Fluid Removal (PFR) recorded from system GUI display hourly and before ending treatment
- 6. Unintended Patient Fluid Loss/Gain recorded from system GUI display at least every 1 hour and before ending treatment

5.8.2.10 Prismaflex Alarms Related to Fluid Balance

- 1. Alarm type (Caution: Flow Problem, Caution: Loss Limit Reached or Caution: Gain Limit Reached)
- 2. Operator Set Limit for Unintended Patient Fluid Loss/Gain (mL/1h)

5.8.2.11 Treatment and Outcome Data at end of study treatment

- 1. Total Prescribed Dose
- 2. Total Delivered Dose
- 3. Attainment of Dry weight (yes/no)
- 4. Attainment of Metabolic control (yes/no)
- 5. Continued need for RRT (yes/no)
- 6. Death (yes/no)
 - a. Time of Death

- b. Date of Death
- c. Cause of Death

5.8.2.12 Adverse Events and Unanticipated Adverse Device Effect Information

- 1. Adverse Event
- 2. Start and Stop Date/Time
- 3. Causality
- 4. Seriousness
- 5. Action Taken
- 6. Outcome

5.8.2.13 Vital Signs

- 1. Height
- 2. Daily Weight
- 3. Pulse Rate
- 4. Respiratory Rate (Spontaneous or Mechanically Ventilated)
- 5. Temperature (location where temperature obtained)
- 6. Blood Pressure
- 7. Mean Arterial Pressure

5.8.2.14 Concomitant Medications

- 1. Medications up to 7 days prior to enrollment (medication name, minimum dose, maximum dose, frequency, route, start date and stop dates)
- 2. Medications taken during treatment, including any prescribed to treat an AE (medication name, minimum dose, maximum dose, frequency, route, start and stop dates).

5.9 Sampling Schedule

Patients will be treated for a minimum period of 24 hours with the measurement of BUN and creatinine at 12 hour intervals during dialysis treatment, see sampling schedule in Prismaflex HF20 Set & Prismaflex® System Software Version 7.10 and 7.20 Page 7 of 60

Gambro 1463, NCT#: 02561247: Clinical Trial Protocol Amendment 6.1 2017 DEC 06

| Table 1. Blood Sampling Schedule | | | | |
|----------------------------------|--|--|--|--|
| Solute | Prior to HF20 CRRT* | At Initiation of HF20 CRRT** | During HF20 CRRT | End of HF20 CRRT (if after 24 hour & between 12 hour interval) |
| Hemoglobin | Up to 24 hours prior to initiation of CRRT | As determined by local standard of care | As determined by local standard of care | N/A |
| BUN | Up to 24 hours prior to initiation of CRRT | Within 1hr prior to or within 15 minutes after CRRT initiation. | At +/- 1 hr of 12, 24, 36, 48, 60, & 72 hours | use previous 12 hour interval labs |
| FUN | NA | Within 1hr prior to or within 15 minutes after CRRT initiation. | At +/- 1 hr of 12, 24, 36, 48, 60, & 72 hours | use previous 12 hour interval labs |
| Creatinine | Up to 24 hours prior to initiation of CRRT | Within 1hr prior to or within 15 minutes after CRRT initiation. | At +/- 1 hr of 12, 24, 36, 48, 60, & 72 hours | use previous 12 hour interval labs |
| Bicarbonate | Up to 24 hours prior to initiation of CRRT | Within 1hr prior to or within 15 minutes after CRRT initiation. | At +/- 1 hr of 12, 24, 36, 48, 60, & 72 hours. | use previous 12 hour interval labs |
| Sodium | Up to 24 hours prior to initiation of CRRT | Within 1hr prior to or within 15 minutes after CRRT initiation. | At +/- 1 hr of 12, 24, 36, 48, 60, & 72 hours | use previous 12 hour interval labs |
| Potassium | Up to 24 hours prior to initiation of CRRT | Within 1hr prior to or within 15 minutes after CRRT initiation. | At +/- 1 hr of 12, 24, 36, 48, 60, & 72 hours | use previous 12 hour interval labs |

| Table 1. Blood Sampling Schedule | | | | |
|--|--|--|---|--|
| Solute | Prior to HF20 CRRT* | At Initiation of HF20 CRRT** | During HF20 CRRT | End of HF20 CRRT (if after 24 hour & between 12 hour interval) |
| Chloride | Up to 24 hours prior to initiation of CRRT | Within 1hr prior to or within 15 minutes after CRRT initiation. | At +/- 1 hr of 12, 24, 36, 48, 60, & 72 hours | use previous 12 hour interval labs |
| Phosphorous | Up to 24 hours prior to initiation of CRRT | Within 1hr prior to or within 15 minutes after CRRT initiation. | At +/- 1 hr of 12, 24, 36, 48, 60, & 72 hours | use previous 12 hour interval labs |
| Albumin | Up to 24 hours prior to initiation of CRRT | Within 1hr prior to or within 15 minutes after CRRT initiation. | At +/- 1 hr of 12, 24, 36, 48, 60, & 72 hours | use previous 12 hour interval labs |
| B2M | NA | Within 1hr prior to or within 15 minutes after CRRT initiation. | At +/- 1 hr of 24,48, & 72 hours | use previous 12 hour interval labs |
| ACT (Applies to heparin use only) | NA | As determined by local standard of care | As determined by local standard of care | As determined by local standard of care |
| PTT (Applies to heparin use only) | NA | As determined by local standard of care | As determined by local standard of care | As determined by local standard of care |
| APTT (Applies to heparin use only) | NA | As determined by local standard of care | As determined by local standard of care | As determined by local standard of care |
| Total Ca | NA | As determined by local standard of care | As determined by local standard of care | NA |
| Extracorporeal Circuit ionized calcium (Not indicated when heparin or no anticoagulation are used) | NA | NA | As determined by local standard of care | NA |
| Patient Ionized Calcium (Not indicated when heparin or no anticoagulant are used) | NA | NA | As determined by local standard of care | NA |

| Table 1. Blood Sampling Schedule | | | | |
|----------------------------------|------------------------|---------------------------------|---------------------|--|
| Solute | Prior to HF20 CRRT* | At Initiation of HF20 CRRT** | During HF20 CRRT | End of HF20 CRRT (if after 24 hour & between 12 hour interval) |

* Labs up to 24 hours prior to CRRT are required, unless the patient presents directly to ICU with immediate need for CRRT. Patient must meet all laboratory based inclusion criteria prior to starting treatment.

** "At initiation of CRRT" samples must be obtained within 1 hour prior to or within 15 minutes after treatment initiation. Labs drawn more than 1 hour prior to initiation will not be acceptable.

| Table 2. Vital Signs & Fluid Overload Assessment Schedule | | | | |
|---|-----------------------------------|--|---|---|
| Parameter | 12-24 Hours Prior to HF20 CRRT | At Initiation of HF20 CRRT – Baseline | During HF20 CRRT | End of HF20 CRRT (& if prior to 72 hours) |
| BP (mmHg) | Within 24 hrs prior to CRRT | Within 1hr prior to or within 15 minutes after CRRT Initiation | Hourly (± 15 minutes) | At End |
| MAP (mmHg) | Within 24 hrs prior to CRRT | Within 1hr prior to or within 15 minutes after CRRT Initiation | Hourly (± 15 minutes) | At End |
| Degree of Fluid Overload* | Within 24 hrs prior to CRRT | Within 1hr prior to or within 15 minutes after CRRT Initiation | 12, 24, 36, 48, 60, & 72 hours(± 1 hour) | At End |

* Degree of Fluid Overload assessment = [fluid intake (L) – fluid output (L) / ICU admission wt (Kg)]×100%

** Re-assess and record baseline measurements if CRRT is being re-initiated (clot/interruption)

[figure not shown]

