6.1 Anticipated Adverse events (AE)

The anticipated adverse effects for this study have been identified in the list below.

- Air embolism
- Coagulation of the dialyzer/extracorporeal circuit resulting in blood loss
- Bradycardia
- Cramping
- Disequilibrium syndrome
- Dizziness
- Electrolyte Imbalance
- Excessive weight loss
- Fluid imbalance
- Hemodialyzer blood leak resulting in blood loss
- Hemolysis
- Hypersensitivity or Allergic Reactions "First Use Reaction"
- Hypertension
- Hypervolemia
- Hypotension
- Hypothermia
- Hypovolemia
- Infection
- Nausea
- Pyrogen Reaction
- Tachycardia
- Vomiting
- Bleeding

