### **5.1.1 Baseline Definition**

All baseline values will be collected during the study visit in which study CRRT treatment is initiated. Baseline measure for laboratory assessments is defined as within 1 hour prior to or within 15 minutes after the initiation of CRRT.

Baseline values for BUN will be utilized in the primary endpoint analysis while creatinine and bicarbonate baseline values will be utilized in the secondary endpoint analysis.

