ACT (Applies to heparin use only)	N/A	As determined by local standard of care	As determined by local standard of care	As determined by local standard of care
PTT (Applies to heparin use only)	N/A	As determined by local standard of care	As determined by local standard of care	As determined by local standard of care
APTT (Applies to heparin use only)	N/A	As determined by local standard of care	As determined by local standard of care	As determined by local standard of care
Total Calcium	N/A	As determined by local standard of care	As determined by local standard of care	N/A
Extracorporeal Circuit ionized calcium (Not indicated when heparin or no anticoagulation are used)	N/A	N/A	As determined by local standard of care	N/A
Patient Ionized Calcium (Not indicated when heparin or no anticoagulant are used)	N/A	N/A	As determined by local standard of care	N/A

\* Labs up to 24 hours prior to CRRT are required, unless the patient presents directly to ICU with immediate need for CRRT. Patient must meet all laboratory based inclusion criteria prior to starting treatment.

\*\* "At initiation of CRRT" samples must be obtained within 1 hour prior to or within 15 minutes after treatment initiation. Labs drawn more than 1 hour prior to initiation will not be acceptable.

Table 3. Vital Signs and Fluid Overload Assessment Schedule

Parameter	Prior to CRRT	At Initiation of CRRT - Baseline	During CRRT	End of CRRT (& if prior to 72 hours)
BP (mmHg)	Within 24 hours prior to CRRT	Within 1 hour prior to or within 15 minutes after CRRT Initiation	Hourly (± 15 minutes)	End of Treatment (± 15 minutes)
MAP (mmHg)	Within 24 hours prior to CRRT	Within 1 hour prior to or within 15 minutes after CRRT Initiation	Hourly (± 15 minutes)	End of Treatment (± 15 minutes)
Degree of Fluid Overload*	Within 24 hours prior to CRRT	Within 1 hour prior to or within 15 minutes after CRRT Initiation	At +/- 1 hour of 12, 24, 36, 48, 60, & 72 hours	End of Treatment (± 15 minutes)

\* Degree of Fluid Overload assessment = [fluid intake (L) - fluid output (L) / ICU admission weight (Kg)]×100%

\*\* Re-assess and record baseline measurements if CRRT is being re-initiated (clot/interruption)

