### 13.4 Vital Signs

Any abnormal vital sign values will be reported as adverse events if deemed clinically significant by the primary investigator. Summary tables will be generated for all recorded time points of all vital sign parameters and will include change from baseline for post baseline time points. Shift tables will also be generated to analyze any changes

from baseline in low, normal or high vital sign values. All vital sign values will be summarized as continuous values utilizing: minimum, maximum, median, mean and standard deviation along with the number of observations analyzed. All vital signs for all time points will be listed for all patients.

Summary tables and listings for vital signs will be provided for the FAS only.

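### The BP and MAP baseline may be read up to 15 minutes after CRRT starts, so an on-treatment value can become the reference for the vital-sign change summaries

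*Protocol*

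**What the plan says.** Protocol Table 2 (section 5.9) has a column for initiation of HF20 CRRT that it labels as baseline. For BP and MAP the permitted time is "Within 1hr prior to or within 15 minutes after CRRT Initiation". SAP Table 3 (section 7.5) carries this over: "Within 1 hour prior to or within 15 minutes after CRRT Initiation". During treatment, BP and MAP are read hourly with a tolerance of 15 minutes. An earlier reading is taken "Within 24 hrs prior to CRRT", but it stands in a separate column and is not the baseline.

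The SAP's definition in words, section 5.1.1, gives a window only for laboratory values: "Baseline measure for laboratory assessments is defined as within 1 hour prior to or within 15 minutes after the initiation of CRRT". For vital signs it says only that baseline values come from the visit at which study CRRT is initiated. No text says that a pre-start reading is preferred, or which reading to use if there is one on each side of the start.

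SAP 13.4 states that the vital-sign summary tables "will include change from baseline for post"-baseline time points, and it also plans shift tables across low, normal and high. The change-from-baseline table (14.3.4.1) is in both lists of tables in the SAP. The shift table (14.3.4.2) is in the Section 16 list but not in the second list that follows it.

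A footnote to both schedules asks sites to reassess and record baseline measurements if CRRT is re-initiated. It does not say which baseline the tables then use.

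**The concern.** A reading between 0 and 15 minutes after initiation is an on-treatment reading, yet it qualifies as baseline. A connection effect on blood pressure would be expected in just those minutes. Hypotension and hypovolaemia are anticipated events in Protocol 6.1. The documents' own figures make some effect plausible in the smallest children. The circuit holds 60 mL (Protocol 3.3) and SAP section 8 takes blood volume as 70 mL/kg, so at 8 kg the circuit is 60/(70 × 8) = 60/560 = 10.7% of blood volume. This makes a fall plausible; it does not show that one occurs.

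The study has one group, so the within-child change is the only comparison that the vital-sign tables offer. If the reference value already contains the fall, the worsening cannot appear as a change. For falls the error runs one way, towards apparent haemodynamic stability, and its size depends on which side of the start a site happens to take its reading.

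**Working it through.** The documents state no figure for this quantity, so there is nothing to reproduce. The check sets the windows side by side and then works out the bias algebraically.

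**Timing.**
- Baseline window: −60 to +15 minutes (Protocol Table 2, SAP Table 3).
- First scheduled hourly reading: 60 ± 15, that is 45 to 75 minutes.
- Overlap of the baseline window with treatment: 0 to +15 minutes.

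**One child (assumed values).** MAP is 60 mmHg before connection, 45 at +10 minutes and 50 at 1 hour.
- Pre-start baseline: 50 − 60 = −10 mmHg.
- Baseline at +10 minutes: 50 − 45 = +5 mmHg.
- Difference: 15 mmHg, with the sign reversed.

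**Group mean.** Let *D* be the fall at connection, *r* the share of it still present at 1 hour, and *f* the share of children whose baseline is read after the start, during the fall. For simplicity every child has the same *D* and *r*.
- True mean change = −*rD*.
- Tabulated mean change = (1 − *f*)(−*rD*) + *f*(−*rD* + *D*) = −*rD* + *fD*.
- Bias = *f* × *D*, whatever the value of *r*.

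Bias in mmHg for assumed values:

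| *f* | *D* = 10 | *D* = 15 | *D* = 20 |
|---|---|---|---|
| 10% | +1.0 | +1.5 | +2.0 |
| 25% | +2.5 | +3.75 | +5.0 |
| 50% | +5.0 | +7.5 | +10.0 |
| 100% | +10 | +15 | +20 |

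For *D* = 15 and *f* = 50%:
- fall fully present at 1 hour: true −15, tabulated −7.5;
- half present: true −7.5, tabulated 0;
- resolved: true 0, tabulated +7.5, a rise that did not happen.

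If 10 of 30 children were read during such a fall, the bias would be 10/30 × 15 = +5 mmHg. With every baseline taken before the start, *f* = 0 and the bias is 0.

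**Shift table.** A child who is normal before connection and low when the baseline is read enters in the low baseline row. The child can then appear as low-to-low or low-to-normal, but not as normal-to-low.

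**The case against.** The strongest reply is that safety in this trial is not judged on these tables. The safety endpoint (Protocol 2.4) is fluid-balance alarms, AEs, SAEs and device deficiencies. No formal safety analysis is planned, and the vital-sign tables have no threshold. That stands, and it limits the priority.

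A reader might infer that a hypotensive episode at connection would be lost from the trial. The documents do not support that:
- AEs are collected from consent. An abnormal vital sign is an AE if it needs intervention or leads to discontinuation (Protocol section 6), or if the investigator judges it clinically significant (SAP 13.4). None of this depends on which reading is called baseline.
- The low value itself would appear in the baseline vital-signs table (14.1.5), in the by-patient listing and in the low row of any shift table. Only the worsening is hidden.
- BP and MAP at ICU admission are also collected (Protocol 5.8.2.9), so the screening value is not the only pre-treatment reading.

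Nor would a first-use reaction disappear. It is an anticipated AE, not a row in a change or shift table, and only its blood pressure component could be absorbed into baseline. Pulse is not in Table 2 or Table 3, so tachycardia and bradycardia lie outside the quoted window. The schedule of events does, however, give vitals at initiation as hourly with a 15-minute tolerance, which also admits a post-start reading.

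That a re-recorded baseline replaces the first is also an inference. The footnote says to record it, not to substitute it, and SAP 5.1.1 points to the visit at which CRRT is initiated. What stands is that no rule settles the matter.

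Finally, hypertension is an anticipated event too, and a rise at connection read as baseline would bias the change downwards. The direction stated here applies to falls.

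**Conclusion.** The point holds in a limited form. Both schedules allow an on-treatment BP or MAP to be the reference for the change-from-baseline summaries in SAP 13.4, and for the shift table if it is produced. A fall read as baseline would show as no change or as a rise. The loss of visibility matters most for a fall that needed no intervention and was not judged clinically significant, since such a fall might not be recorded as an AE.

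The size is *f* × *D*. The documents give neither the share of children read after start nor the fall at connection, so every mmHg value above is an illustration. The reasoning about direction needs only that some falls occur at connection and that some baselines are read during them; the documents do not show how often either happens. No primary or secondary efficacy result uses baseline BP. Priority is minor to moderate.

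**What to change.** In Protocol Table 2, SAP Table 3 and SAP 13.4:

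1. Define baseline for BP and MAP, and for the other vital signs, as the last reading before CRRT start within the existing 1-hour window.
2. Classify any reading after the start as on-treatment and include it in the SAP 13.4 summaries.
3. State that a value re-recorded at re-initiation does not replace the first baseline in the change-from-baseline tables.
4. Confirm whether the vital-sign shift table (14.3.4.2) will be produced, and make the two lists of tables agree.

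The laboratory window, and with it the primary endpoint, is unchanged.

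The cost is wording in two tables and one derivation rule, which needs reading times to be recorded. No new procedure is required, because a pre-start reading is already within the permitted window. A few children may have no reading in the hour before start; their baseline would then be missing, and their number should be reported. The change removes the bias but does not improve detection of brief falls: a transient fall between scheduled readings, the first of which is due at 45 to 75 minutes, would still not be seen in these tables.

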5.10 Emergency Procedure

[figure not shown]
The investigators are in charge of ensuring that the required procedures and skills are available in the event of any emergency situation during the study.

An SAE may constitute an emergency situation. As a consequence, any emergency situation developing during the clinical study period must be immediately reported to Gambro, whether directly related to the study or not.

All SAEs regardless of their relationship to the study product will be submitted to sponsor by the Investigator or designee within 24 hours of becoming aware of the event.

In case of emergency, one of the following people shall be contacted in the shortest possible time and in the following order of priority:

6. ADVERSE EVENTS, SERIOUS ADVERSE EVENTS AND UNANTICIPATED ADVERSE DEVICE EFFECTS

An AE is any untoward medical occurrence in a patient or clinical investigational patient administered a study product and which does not necessarily have a causal relationship with the treatment or device. An AE can therefore be any unfavorable and unintended sign (including an abnormal laboratory function), symptom (rash, pain, discomfort, fever, dizziness, etc.), organ dysfunction (cardiovascular failure, pancreatitis, etc.), systemic illness (eg, sepsis), or outcome of death temporally associated with the use of the study product, whether or not the event is considered associated with the study product.

- Laboratory and vital sign abnormalities qualify as AEs if medical intervention is required to treat or address the abnormality, if the patient must be discontinued from the study due to the abnormality, or if the value exceeds specific limits defined by the protocol as qualifying it as an AE.
- An elective procedure/surgery that occurs during the course of a study, but is being performed for a documented pre-existing condition and was pre-planned prior to study entry will not qualify as an AE. If, however, the pre-existing condition unexpectedly deteriorates during the study requiring the procedure/surgery to be performed earlier than planned, the condition for which the procedure/surgery is being performed will qualify as an AE.

Adverse events will be collected starting from the time the patient signs the ICF until the end of the Prismaflex HF20 Set study treatment. During the course of the study, the Investigator or designee shall routinely monitor each patient for the occurrence of any AE. Routine monitoring should include regular communication with the trial patient, review of laboratory results and assessment of anticoagulation, dialysis access and medication use. If an AE occurs, a full description of the event should be recorded including the date of onset, severity, time course, description, actions taken and causal relationship of the AE to the study product(s). Investigators should review and reference the Causality definitions below when determining the relationship of the AE to the study product. The investigators may also discuss the event(s) with the sponsor Medical Monitor, but the Investigator must make, document and report the relationship for every AE. All AEs must be documented in source documents and on the eCRFs, no matter how common they are for a particular patient and regardless of the causality assigned by the Investigator.

All AEs and SAEs, regardless of relatedness, should be actively solicited and recorded by the Investigator or designee at defined visits throughout the course of the study. Additionally, any AE voluntarily reported by the patient should be recorded and verified by the Investigator or designee on the appropriate source documents and eCRF pages. Each SAE will be documented on a separate SAE report form.

The outcome/resolution of all AEs and SAEs will be determined by the Investigator and documented on the AE eCRF and the SAE report form. Investigators will be instructed to follow all AEs/SAEs as follows: Unrelated AEs will be followed until resolution or until the end of the study, whichever occurs first. Adverse drug/device effects (related AEs) and all SAEs (related or not) will be followed until resolution or stable, including following the patient after the end of the study if necessary. The outcome categories that can be chosen on the eCRF by the Investigator include: Fatal, Not recovered/Not resolved (this outcome is reached for AEs which are ongoing when the patient's end of study is due to death related to another AE), Recovering/Resolving (this outcome is reached for AEs which are ongoing at the patient's end of study), Recovered/Resolved with Sequelae (if there are some residual effects caused by the event), Recovered/Resolved, and Unknown.

All SAEs regardless of their relationship to the study product will be submitted to sponsor by the Investigator or designee within 24 hours of becoming aware of the event.

An AE can result from the use of the study product in accordance with the protocol, as well as from an accidental or intentional misuse of the study product or any other treatment error such as unintentional administration or use of another product during the course of the study. Each investigator is to inform sponsor as soon as possible of all AEs or of any Unanticipated Adverse Device Effects (UADEs) associated with the Prismaflex HF20 Set and/or the Prismaflex Control Unit Software Version 7.10 and 7.20 that occurs during the course of the study/treatments, by telephone or email. Each investigator is to complete the electronic AE form in the EDC and, if applicable, the Serious Adverse Event (SAE) Report form and email it to the Prismaflex HF20 study email box. All SAEs and UADEs must be reported to the sponsor and the Data Safety Monitor. All UADEs must be reported to the reviewing IRB as soon as possible, but not later than ten working days after the investigator first learns of the effect per 21 CFR Part 812.150 (1).

Anticipated AEs and UADEs are defined as follows:

